2.1.1.5 Prior therapy

\geq 2 weeks must have elapsed since local palliative XRT (small port) or other substantial BM radiation;

\geq 24 weeks must have elapsed since prior TBI, craniospinal XRT, or if \geq 50% radiation of pelvis;

\geq 12 weeks must have elapsed since stem cell transplant or infusion without TBI and no active graft vs. host disease;

\geq 3 weeks must have elapsed from last dose of myelosuppressive chemotherapy (six weeks for nitrosoureas);

at least 3 half-lives must have elapsed since monoclonal antibody;

(<https://members.childrensoncologygroup.org/Disc/devtherapeutics/default.asp> for listing of monoclonal antibody half-lives.)

\geq 7 days must have elapsed from the last dose of biologic agents.

\geq 7 days since the completion of therapy with a growth factor

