The most profound toxicity seen was hemorrhage. The tendency for bleeding occurred infrequently and in early reports was attributed to thrombocytopenia and accounted for 3 deaths out of 84 patients treated (33). Subsequent studies showed that bleeding occurred early in treatment at about day 4 and was dose related occurring in 5.4% of 1150 patients treated at 30 mcg/kg/day or less (25). This time frame is significantly shorter than what is typically seen for chemotherapy induced thrombocytopenia. In addition, it appears as though the platelet count remained >20,000/mcL in most of the cases of hemorrhage in the literature. Subsequent to these studies, it was determined that mithramycin treatment caused a decrease in coagulation factors II, V, VII and X (34). In addition, subsequent studies revealed that mithramycin causes abnormal platelet adhesion in the setting of a normal platelet count consistent with a platelet adhesion

molecule deficiency (35). It is notable, that in addition to inhibiting EWS-FLI1, mithramycin is known to inhibit the SP1 transcription which is known to drive the biosynthesis of coagulation factors as well as platelet adhesion glycoproteins. Nevertheless, in all the cases of hemorrhage reported in the literature, it is not clear if the patients were taking any anti-coagulation medications, what type of blood product support was provided, and how effective the blood product support was in that era of treatment. In particular, it is not clear if patients received platelets in the setting of a normal platelet count as would be required for an acquired platelet adhesion defect. Regardless of the etiology, this side effect must be approached with extreme caution.

Another rare but significant side effect described in the literature is the report of toxic epidermal necrolysis that has been associated with mithramycin treatment (36, 37). This side effect is reported in two separate case reports but was omitted in the package insert from Pfizer (37) and appears to begin with plethora and non-specific skin findings. The incidence of this side effect is unclear, however due to the substantial nature of this reaction, all skin eruptions should be approached with significant caution.

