2.1.1.6 Recovered from acute toxicities of prior therapy to \leq Grade 1; specifically

a) Hematologic and Coagulation Parameters

- i. Peripheral ANC \geq 1000/mcL
- ii. Platelets \geq 75,000/ mcL (transfusion independent)
- iii. Hemoglobin \geq 8 g/dL (PRBC transfusions permitted)
- iv. Normal PT/PTT with the exception of a lupus anti-coagulant, which is permitted, may be corrected with Vitamin K administration or transfusion. Fibrinogen \geq the lower limit of normal.

b) Hepatic Function

- i. Bilirubin (total) \leq 1.5 X upper limit of normal (ULN)
- ii. ALT (SGPT) \leq 2.5 X ULN
- iii. Albumin $>$ 2 g/dL

c) Renal Function

- i. Creatinine clearance \geq 60 mL/min/1.73 m², or serum creatinine base on age and gender as follows:

Age (years)	Maximum Serum Creatinine (mg/dL)	
2 to $<$ 6	0.8	0.8
6 to $<$ 10	1	1

10 to < 13	1.2	1.2
13 to < 16	1.5	1.4
≥ 16	1.7	1.4

- Normal calcium, magnesium and phosphorus (can be on oral supplementation)

2.1.1.7 Cardiac Function: Left ventricular ejection fraction (EF) within normal institutional limits by Echocardiogram MUGA or cardiac MRI.

2.1.1.8 Ability to give informed consent. For patients <18 years of age their legal guardian must give informed consent. Pediatric patients will be included in age-appropriate discussion in order to obtain verbal assent.

2.1.1.9 Female and male patients (and when relevant their partners) must be willing to practice birth control (including abstinence) during and for two months after treatment, if of childbearing potential during sexual contact with a female of childbearing potential.

2.1.1.10 A durable power of attorney (DPA) will be offered to all patients ≥ 18 years old.

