2.2 SCREENING EVALUATION

2.2.1 General

Pre-treatment blood test should be performed within 7 days and imaging studies within 2 weeks prior to enrollment on the trial unless otherwise stated. The evaluations required prior to starting treatment are listed in table form in Appendix 3 Study Calendar.

HISTORY AND PHYSICAL EXAMINATION: including documentation of height and weight (average of 3 measurements on the same day), measurable disease, vital signs (blood pressure, heart rate, respiratory rate, temperature), performance status, history of bleeding disorder, HIV, HBV, HCV, and signs and symptoms within one week of enrollment.

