10.1.6 Contraindications

The following medications are contraindicated:

- Anticoagulants, coumarin- or indandione-derivatives
- Heparin other than heparin flushes
- Thrombolytic agents
- Anti-inflammatory drugs, nonsteroidal (NSAIDs) or aspirin or salicylate-containing products, which may increase risk of hemorrhage
- Dextran
- Dipyridamole
- Sulfapyrazone
- Valproic acid

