Kofman, s (40)	1964	22 10 15 Much younger 3 16 yo 2 23 yo	? of redundant patients 3 ESFT reported (2 repeats)				Not systematically reported -thrombocytopenia seen			
Curreri, AR(28)	1960	36 pts no age	Variety A synovial	5/26 Embryonal CA 2 Chorio 1 Wilms 1 Breast 1 (all at 40 ug/day or more)	25, 30, 35, 40, 50, 60, 70, 80, 90	Daily times 5 q 5-7 wks	n/v. thrombocytopenia, hemorrhage, hepatic damage (Transaminases, PT, Alk Phos) Hemorrhage described in some detail LFT changes common at doses >50 mcg/kg/day (increase AP, GOT, decrease PT); 2 pts SGOT of 800 U		50 μ g/dose	

Abbreviated Title: Ph I/II Pediatric Mithramycin

Version Date: 11/09/2016

Spear (29)	1963	58 patients (only 29 with performance status >50)	Variety of adult melanoma, bronchogenic CA, hepatoma	NONE	50 ug/kg/dau	50 x 1 then 60 ug/kg/day q week x 8	N/V, severe diarrhea in 3, LFTs -thrombocytopenia in 1 patient -GI hemorrhage causing death in 1	N/A	N/A	N/A
Dube (55)		7 pts adults	Advanced metastatic cancer		25 to 30 mcg/kg/day as cont. infusion	For 5-13 days until toxicity	In all pts hematologic and hepatic toxicity: decrease WBC and plt, increase SGOT			
Package insert Pfizer (25)	1971	1600 patients	Testicular CA		25 ug/kg/day over 12 hours daily x 8 q month dilute in 1L of d5 and give over 4-6hrs	Q month	Contraindicated: thrombocytopenia, coagulopathy, poor bone marrow, follow PLTs, PT and bleeding time -hemorrhagic syndrome is dose related if 30 ug/kg/day or less 10 or fewer bleeds -drug mortality rate is 1.6% IF >30 12% bleeding with mortality rate of 5.7% COMMON: Anorexia, N/V, stomatitis LESS COMMON: Fever, drowsiness, lethargy, malaise, H/A, depression, phlebitis, flushing, skin rash LABS: Thrombocytopenia, leucopenia (6%), increased clotting, bleeding time, abnormal clot retraction, LFTs, AP, LDH, bili Renal, Increased BUN, CR and proteinuria Hypocalcemia, hypophosphatemia, hypokalemia			

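### Section 2.1.1.5 gives substantial marrow radiation the same 2-week washout as a small palliative port, shorter than the 3 weeks it requires after myelosuppressive chemotherapy

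*Combined protocol and SAP*

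**What the plan says.** Section 2.1.1.5 (Prior therapy) lists minimum intervals between earlier treatment and entry. One line covers two kinds of radiotherapy: at least "2 weeks must have elapsed since local palliative XRT (small port) or other substantial BM radiation". Two other lines are the natural comparators. For chemotherapy, at least "3 weeks must have elapsed from last dose of myelosuppressive chemotherapy (six weeks for nitrosoureas"). For large fields, at least "24 weeks must have elapsed since prior TBI, craniospinal XRT, or if" half or more of the pelvis was irradiated. No other section sets an interval for substantial marrow radiation, defines the term, or explains the 2 weeks.

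Section 2.1.1.6 adds count limits. Patients must be "Recovered from acute toxicities of prior therapy to" grade 1 or less, with a neutrophil count of at least 1000/mcL and a platelet count of at least 75,000/mcL without transfusion. Section 2.2.1 sets when these are measured: "Pre-treatment blood test should be performed within 7 days and imaging studies within 2 weeks prior to enrollment on the trial".

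On marrow fitness for this drug, the package-insert row of Appendix 1 reads "Contraindicated: thrombocytopenia, coagulopathy, poor bone marrow". Section 10.1.6 opens with "The following medications are contraindicated" and lists only drugs.

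**The concern.** A washout list should ask for a longer wait after a larger insult to the marrow. This one does so elsewhere, with 3 weeks for myelosuppressive chemotherapy, 6 for nitrosoureas and 24 for the largest radiation fields. The exception is radiation described as substantial to marrow, which is placed with the mildest radiotherapy on the list. A small port is hardly an example of substantial marrow radiation, so two criteria may have been merged by accident. That is an inference; the protocol does not say so.

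The first thing at stake is patient safety. Phase I takes children from 12 months of age, and the drug's package insert warned against use in patients with poor marrow. The second is how phase I toxicity is read. In Section 3.1.1 the non-hematologic definition of dose-limiting toxicity requires a possible, probable or definite relation to mithramycin. The hematologic definition states no such condition, and it includes platelets that have not returned to 75,000/mcL by day 42 of a cycle. Slow recovery caused by earlier radiation could meet that definition.

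**Working it through.** There is no sample-size or error-rate figure to reproduce. The check sets the intervals side by side and then asks what else in the plan screens the marrow.

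1. **Intervals in Section 2.1.1.5, in days.** Small-port palliative radiotherapy: 2 × 7 = 14. Other substantial marrow radiation: 14. Myelosuppressive chemotherapy: 3 × 7 = 21. Nitrosoureas: 6 × 7 = 42. Total-body, craniospinal or at least half-pelvis radiation: 24 × 7 = 168.

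2. **Differences for substantial marrow radiation.** Against the small port: 14 − 14 = 0 days. Against chemotherapy: 21 − 14 = 7 days shorter. Against nitrosoureas: 42 − 14 = 28 days shorter. Against the large fields: 14/168 = 1/12.

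3. **What else screens the marrow at entry.** The counts in Section 2.1.1.6 exclude cytopenia present when the sample is taken. They do not measure reserve. The protocol treats counts and time as separate requirements, because it keeps the chemotherapy and large-field washouts alongside the same count limits. Section 2.1.2.1 adds a general exclusion by investigator judgment. The marrow contraindication in Appendix 1 is not carried into Section 10.1.6.

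4. **What manages the patient after entry.** Section 3.1 requires admission during cycle 1 dosing. Section 3.5.1.4 requires a blood count daily on days 2 to 7, then twice weekly in cycles 1 to 3. Section 4.1 supports platelets at 25,000/mcL or above. All of this applies to the phase I children.

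5. **Route into the phase I decision.** Under Section 3.1.2, one dose-limiting toxicity among 3 patients expands the cohort to 6, and 2 or more of 6 means the maximum tolerated dose has been exceeded. A radiation-related platelet delay counted under Section 3.1.1 would enter that tally. The documents give neither the number of such patients nor the chance of delayed recovery, so no probability can be calculated.

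6. **Effect of a 21-day floor.** Only entries on days 14 to 20 after such radiation change. The longest added wait is 21 − 14 = 7 days.

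**The case against.** The strongest reply is that the plan already protects these patients. The largest fields are at 24 weeks. Entry needs adequate counts, with platelets unsupported by transfusion, and growth factors must have stopped at least 7 days earlier. A falling count would be seen from day 2 in an inpatient. The contraindication is an undefined fragment in a literature table, tied to 25 mcg/kg/day, whereas this trial gives 13 to 17.5. All of this stands and reduces the likely harm. It does not explain why radiation called substantial to marrow has the small-port interval.

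A second reply is that 3 weeks is borrowed from a different exposure. That is also right. The documents contain no correct interval for this radiation; 3 weeks is only the list's own comparator, and the intended value could be longer. Nor would the floor remove every gap, because the qualifying count could still be up to 7 days old at enrollment.

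On dose-limiting toxicity, Section 3.3 mentions relation to mithramycin when saying which events lead to the drug being held. One could argue that attribution is understood throughout, but the hematologic definition in Section 3.1.1 does not say so.

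Two stronger readings should be set aside. A reader might link the short washout to Section 1.2.3, where "bleeding occurred early in treatment at about day 4", and fear an overlap with low platelets after radiation. That section points elsewhere: it calls the timing too early for the usual chemotherapy-induced thrombocytopenia, reports platelets above 20,000/mcL in most hemorrhages, and cites reduced clotting factors and abnormal platelet adhesion. A reader might also infer that a radiation nadir is still to come at day 14. No section gives the timing of such a nadir.

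**Conclusion.** The point holds as an internal inconsistency with a safety consequence, and it should be corrected. Substantial marrow radiation has a washout equal to that for a small port, 7 days below that for myelosuppressive chemotherapy and one-twelfth of that for the largest fields. The safeguards detect or manage cytopenia without testing reserve, so they limit the harm but do not take the place of the interval.

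A distorted maximum tolerated dose might be inferred, but the documents do not support that claim. They show only a possible route through the hematologic definition, of unknown size. The Simon two-stage response rule is unaffected.

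The conclusion assumes that the line means what it says and that at least some enrolled patients will have had such radiation outside the 24-week categories. Their number is not given.

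**What to change.** In Section 2.1.1.5, limit the 2-week line to small-port palliative radiotherapy. Add a separate line for other substantial marrow radiation with an interval no shorter than the 3 weeks required after myelosuppressive chemotherapy. The clinical team should set the final value, which may be longer, and should state which fields count as substantial. The count limits and the definitions of dose-limiting toxicity can stay as they are.

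The cost is a small change to the eligibility wording. At the 3-week floor, a patient who would have entered on days 14 to 20 after such radiation waits at most 7 more days. A longer interval would cost correspondingly more, which matters in refractory disease and is a reason to leave the final figure to the clinical team.

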2.1.1.6 Recovered from acute toxicities of prior therapy to \leq Grade 1; specifically

a) Hematologic and Coagulation Parameters

- i. Peripheral ANC \geq 1000/mcL
- ii. Platelets \geq 75,000/ mcL (transfusion independent)
- iii. Hemoglobin \geq 8 g/dL (PRBC transfusions permitted)
- iv. Normal PT/PTT with the exception of a lupus anti-coagulant, which is permitted, may be corrected with Vitamin K administration or transfusion. Fibrinogen \geq the lower limit of normal.

b) Hepatic Function

- i. Bilirubin (total) \leq 1.5 X upper limit of normal (ULN)
- ii. ALT (SGPT) \leq 2.5 X ULN
- iii. Albumin $>$ 2 g/dL

c) Renal Function

- i. Creatinine clearance \geq 60 mL/min/1.73 m², or serum creatinine base on age and gender as follows:

Age (years)	Maximum Serum Creatinine (mg/dL)	
2 to $<$ 6	0.8	0.8
6 to $<$ 10	1	1

10 to < 13	1.2	1.2
13 to < 16	1.5	1.4
≥ 16	1.7	1.4

- Normal calcium, magnesium and phosphorus (can be on oral supplementation)

2.1.1.7 Cardiac Function: Left ventricular ejection fraction (EF) within normal institutional limits by Echocardiogram MUGA or cardiac MRI.

2.1.1.8 Ability to give informed consent. For patients <18 years of age their legal guardian must give informed consent. Pediatric patients will be included in age-appropriate discussion in order to obtain verbal assent.

2.1.1.9 Female and male patients (and when relevant their partners) must be willing to practice birth control (including abstinence) during and for two months after treatment, if of childbearing potential during sexual contact with a female of childbearing potential.

2.1.1.10 A durable power of attorney (DPA) will be offered to all patients ≥ 18 years old.

2.1.1.11 Eligibility criteria for mandatory serial tumor biopsies

- Age: ≥ 18 years old
- Ewing sarcoma with EWS-FLI1 fusion transcript
- Hematologic and coagulation parameters within 2 days prior to each biopsy: Normal PT/PTT with exception of lupus anticoagulant, platelets ≥75,000/mcL, peripheral ANC ≥750/mcL
- Willing to undergo biopsies, which will only be performed on tumors amenable to percutaneous biopsy ([Error! Reference source not found.](#))

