3.5.1.2 Weight: at baseline and recommended daily days 2 to 7 each cycle

3.5.1.3 A 12-lead EKG will be performed day 1 and 7 of each cycle, and day 4 of cycle 1. All EKGs should be done prior to drug infusion on that day and as close as possible to the time the trough PK is drawn. Document the time the EKG is performed on the PK sheet ([Appendix 4: Pharmacokinetic Worksheet for Mithramycin \(Phase I and Phase II For nursing staff\)](#))

3.5.1.4 Laboratory evaluation:

CBC with differential count daily (starting on day 2 to day 7) during mithramycin administration; then twice weekly during cycles 1-3. During subsequent cycles: CBC with differential count twice weekly during administration, then weekly.

Chemistry: sodium, potassium, chloride, CO₂, creatinine, glucose, BUN, albumin, calcium, magnesium, daily (starting on from day 2 to day 7) during drug administration; then twice weekly during cycles 1-3. During subsequent cycles chemistries are performed weekly.

Liver Function Tests: alkaline phosphatase, ALT/GPT, AST/GOT, total bilirubin, total protein, daily (starting on day 2 to day 7) during drug administration; then twice weekly during cycles 1-3. During subsequent cycles chemistries are performed weekly.

Coagulation Studies: PT/PTT/Thrombin Time, Fibrinogen prior to and once on days 3, 4 or 5 and days 7, 8, or 9 of every cycle. In addition, prior to cycle 1 and 2, 1 mL of plasma will be obtained, filtered through a 0.22 micron filter, frozen and saved for future clinical reference if needed (See [Appendix 8: Plasma samples for clinical purpose](#)).

Pregnancy test for women of child-bearing age: prior to each cycle.

Urinalysis: prior to each cycle.

3.5.1.5 Tumor Measurements:

Disease evaluations will be performed after every EVEN numbered treatment cycle, i.e. cycle 2, cycle 4, etc, and when removed from treatment, when feasible: Assessment of disease sites will be performed using the most appropriate radiological evaluation. This could include a CT scan of chest, abdomen and pelvis and primary tumor, bone scan, FDG-PET or MRI as indicated. A consistent method of disease evaluation will be used throughout the study. Imaging studies used for response evaluation will be sent to the NCI POB for volumetric analysis as secondary endpoint (See **Appendix 9: Imaging studies for volumetric analysis of tumor burden**).

3.5.2 Monitoring after completion of treatment with mithramycin:

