11.7 APPENDIX 7: STUDIES TO BE PERFORMED ON TUMOR TISSUE

Archival tumor tissue

a) Archival paraffin embedded tumor tissue for confirmation of EWS/FLI1 fusion transcript to determine eligibility for phase II portion of trial, and for evaluation of NR0B1 expression in patients with Ewing sarcoma

Archival paraffin embedded tissue, or if paraffin embedded tissue is not available, 5 consecutive unstained slides, should be sent via express carrier to:

[name]
NCI, POB
[name]
[name]
[name]
[contact]

Please notify [name] by e-mail ([contact]) prior to shipment.

[name] will submit these samples to the Laboratory of Pathology for testing.

Tumor tissue from Mandatory tumor biopsies for NR0B1 expression and gene signature (Phase II)

In patients with Ewing sarcoma and EWS-FLI1 fusion transcript \geq 18 years old, who have disease amenable to percutaneous biopsy, and who meet other eligibility criteria for biopsy, a biopsy will be obtained prior to treatment and at steady state on treatment during cycle 1. Patients who meet these criteria will have to agree to the biopsies in order to be able to participate in the trial.

Tumor Biopsies

Willingness to undergo tumor biopsies is required for patients with disease amenable to percutaneous biopsy on this protocol because modulation of molecular targets in tumor biopsies after drug treatment is an important objective of this study.

Baseline biopsies will be performed following patient enrolling on study. If an initial attempt at percutaneous biopsy is unsuccessful, the patient will be given an option to proceed with a repeated attempt at percutaneous biopsy. A separate consent form must be signed for each biopsy procedure, so patients may choose not to undergo subsequent biopsies. If the baseline biopsy is unsuccessful or the patient refuses to undergo subsequent biopsies, no further biopsies will be performed, but the patient will remain on study, receive study medication, and other correlative studies will be performed. Similarly, patients who miss the first dose of drug will not subsequently be biopsied, but will remain on study.

Timing of tumor biopsies

For NR0B1 expression and gene expression signature tumor one tumor biopsy each will be obtained prior to treatment, and day +4 (+/- 1 day) during cycle 1 at steady state on treatment with mithramycin.

Biopsy procedure

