No more than 2 tumor biopsy procedures per patient will be performed by Interventional Radiology. It is preferred that two core biopsies not less than 18-gauge in diameter and at least 1 cm in length are obtained. Only percutaneous biopsies will be performed. No biopsy of lung metastases will be attempted.

It is estimated that there will be between 2-5 million cells from each biopsy. If a site is deemed appropriate for biopsy with minimal risk to the participant by agreement between the investigators and Interventional Radiology, an attempt at biopsy will be made. Determination of a disease site amenable to biopsy will be determined on an individual case basis after discussion with an interventional radiologist. The biopsy procedure to be used in this protocol is described below. Such biopsies can be safely performed as evidenced by literature reports (56) and Medical Oncology Branch experience at the Clinical Center. Risks of the procedure include, but are not limited to, bleeding, infection, pain, and scarring. We will follow Clinical Center Interventional Radiology SOPs for coagulant panel and platelets.

All biopsies will be by percutaneous approach. No biopsy by an invasive (endoscopic, laparoscopic, or surgical) procedure will be performed. Only cutaneous, subcutaneous, or easily accessible parenchymal lesion core biopsies will be performed; however, there will be no core biopsies of lung lesions.

The use of imaging to facilitate biopsies will be decided by members of the Interventional Radiology team and may include ultrasound, CT scan, or MRI. Should CT scan be needed for biopsy, the number of scans for each procedure will be limited to the minimum number needed to safely obtain a biopsy. All cases will be carefully reviewed with the interventional radiologists at NIH who have extensive experience in performing such procedures. Only if the procedure is considered to be low risk will we proceed with tumor biopsy in a given participant.

Biopsy processing:

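### A day 3 on-treatment biopsy can be cleared on PT/PTT drawn before the first mithramycin dose

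*Combined protocol and SAP*

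**What the plan says.** Section 2.1.1.11 lists what must hold before a research biopsy: "Hematologic and coagulation parameters within 2 days prior to each biopsy: Normal PT/PTT with exception of lupus anticoagulant, platelets ≥75,000/mcL", together with a neutrophil minimum. The rule is the same for the pre-treatment and the on-treatment biopsy.

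Appendix 7 times the second biopsy at "day +4 (+/- 1 day) during cycle 1 at steady state on treatment with mithramycin", that is, day 3, 4 or 5. Mithramycin is infused daily on days 1 to 7.

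Section 3.5.1.4 schedules coagulation tests as "PT/PTT/Thrombin Time, Fibrinogen prior to and once on days 3, 4 or 5 and days 7, 8, or 9 of every cycle". Footnote d of the study calendar (Appendix 3) gives the same days, allows extra draws when clinically indicated, and lets the day 1 draw of cycle 1 be skipped if screening coagulation was done within a week of starting drug. No draw is tied to the biopsy, so the day 3-5 draw may come after it. Blood counts, by contrast, are taken daily from day 2 to day 7.

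On the hazard, section 1.2.3 reports a fall in factors II, V, VII and X under mithramycin. For doses of up to 30 mcg/kg/day it adds: "bleeding occurred early in treatment at about day 4 and was dose related occurring in 5.4% of 1150 patients". Its conclusion on hemorrhage reads: "Regardless of the etiology, this side effect must be approached with extreme caution".

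Appendix 7 adds two further controls: "We will follow Clinical Center Interventional Radiology SOPs for coagulant panel and platelets", and "Only if the procedure is considered to be low risk will we proceed with tumor biopsy in a given participant".

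**The concern.** A look-back of 2 days is reasonable for the baseline biopsy, when nothing is changing. For the on-treatment biopsy it can reach back across the start of a drug that the protocol itself says depresses clotting factors. PT/PTT is the part of the gate meant to detect that effect, and a pre-dose sample cannot detect it.

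The stake is patient safety in a procedure done for research. The decision that a biopsy is low risk could rest on a clotting result with no drug exposure behind it. Bleeding of grade 2 or more that does not resolve within 6 hours of treatment also ends mithramycin for that patient (sections 3.3 and 3.7.1).

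**Working it through.** The plan states no figure for this rule, so the check is calendar arithmetic followed by the cost of the remedy.

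**Look-back.** Inputs: biopsy day b = 3, 4 or 5 (Appendix 7); gate samples from day b − 2 to day b, counted in calendar days (section 2.1.1.11); one infusion daily from day 1 (section 3.1). I assume that the sample and the biopsy both precede that day's infusion. Then a sample on day d reflects d − 1 completed infusions, and the patient has had b − 1 by the biopsy.

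| Biopsy day | Oldest sample accepted | Infusions behind that sample | Infusions given by biopsy | Scheduled panel days that satisfy the gate |
|---|---|---|---|---|
| 3 | day 1 | 0 | 2 | 1, 3 |
| 4 | day 2 | 1 | 3 | 3, 4 |
| 5 | day 3 | 2 | 4 | 3, 4, 5 |

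Only the day 3 row admits a sample with no drug exposure. At the nominal day 4, any scheduled panel that satisfies the gate is from day 3 or day 4, so the gap there is small.

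**Two conditions on the day 3 row.**
- On a strict 48-hour reading, a pre-dose day 1 sample qualifies only if the day 3 biopsy is done by the same clock time.
- If the day 1 draw is skipped under footnote d, the screening sample was generally taken before day 1. It is then at least 3 calendar days old on day 3, and the gate itself forces a new sample.

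**Under a rule of biopsy day or day before.** The oldest sample is from day b − 1, which reflects b − 2 infusions: 1, 2 or 3 for b = 3, 4 or 5. The scheduled panel meets this if drawn on day 3 (b = 3), day 3 or 4 (b = 4), or day 4 or 5 (b = 5).

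**Cost in pairs.** Section 8.4 plans up to 20 evaluable pairs and an exact one-sided binomial test at 0.10, comparing 5% with 25%, and states 90% power. Reproduced: the smallest count r with P(X ≥ r | n = 20, p = 0.05) ≤ 0.10 is r = 3. The attained alpha is 0.0755 and the power is P(X ≥ 3 | n = 20, p = 0.25) = 0.909. The documents do not say how many pairs a fresher PT/PTT would cost, so I assume 1 to 3, lost at random. The critical count stays at 3:

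| Pairs | Alpha | Power at 25% |
|---|---|---|
| 20 | 0.0755 | 0.909 |
| 19 | 0.0665 | 0.889 |
| 18 | 0.0581 | 0.865 |
| 17 | 0.0503 | 0.836 |

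**The case against.** The case on the other side is substantial. The problem is confined to one edge of a three-day window, needs the calendar-day reading, and disappears when footnote d removes the day 1 draw. Platelet counts are current because blood counts are daily. Cycle 1 is given in hospital, patients with a bleeding diathesis or on antiplatelet drugs are excluded, and only accessible, non-lung sites are biopsied. The interventional radiology procedures cover clotting tests and platelets and may already demand a fresher sample. Willingness to be biopsied is an entry condition, but each procedure has its own consent, and a patient may decline the second biopsy and stay on study.

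All of this limits the point. None of it, as written, stops a day 1 PT/PTT from clearing a day 3 biopsy. Footnote d permits extra draws but does not require one before the biopsy.

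A reader might go further in four ways that the documents do not support.
- **That on-treatment biopsies in general can be cleared on pre-dose values.** The table above shows that day 4 and day 5 cannot.
- **That the gate needs a platelet-function test.** Section 1.2.3 does say that "mithramycin causes abnormal platelet adhesion in the setting of a normal platelet count". It does not say when in treatment this begins, and nothing in the documents shows that PFA-100 predicts biopsy bleeding.
- **That the fibrinogen limit at entry should be a pass/fail item here.** Section 1.2.3 gives no fibrinogen mechanism.
- **That 5.4% measures the biopsy risk.** It is bleeding during treatment at up to 30 mcg/kg/day, described as dose related. The documents give no biopsy-bleed rate and no bleeding rate at 17.5 mcg/kg.

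**Conclusion.** The point holds in a narrow form. Sections 2.1.1.11 and Appendix 7 together let a day 3 biopsy go ahead on a PT/PTT taken before any drug, after two infusions of an agent that the protocol says lowers clotting factors. It concerns one on-treatment biopsy per biopsied patient, with 12 to 20 pairs planned, and only those done on day 3.

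The conclusion assumes that the look-back is in calendar days (or that the biopsy falls within 48 hours of the sample), that a day 1 sample was drawn, and that the interventional radiology procedures are not tighter. The last cannot be checked. What is shown is a gap in the protocol's wording, not in practice at the site, and the size of any bleeding risk cannot be estimated. Severity is minor and relates to patient safety only; no statistical figure in the plan changes.

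**What to change.** In section 2.1.1.11 and Appendix 7, for the on-treatment biopsy only:

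1. Require the gate PT/PTT to be drawn after mithramycin has started, on the day of the biopsy or the day before, and reviewed before the biopsy.
2. Time the already scheduled day 3-5 coagulation panel to meet this where the days match: day 3 for a day 3 biopsy, day 3 or 4 for day 4, day 4 or 5 for day 5. Thrombin time and fibrinogen on that panel then inform the existing low-risk decision, with no new pass/fail limit.
3. Report the number of on-treatment biopsies omitted for any failed coagulation or platelet criterion next to the NR0B1 inhibition rate.

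The laboratory cost is close to nil, since the panel is mostly a matter of timing. The real cost is that a few pairs may be lost to an abnormal post-dose PT/PTT, with the power loss shown above if losses are random. Omissions could instead track drug effect. The inhibition rate would then be biased by an amount that the documents give no means to size, which is the reason for item 3. If fewer than 12 evaluable pairs are available when the other objectives are met, sections 3.1.3 and 8.4 keep enrollment open, so a lost pair would then mean biopsying another patient.
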